#### 6.4.4.2 Analyses of neutralization assay data

*Primary analyses:* The area-under-the-magnitude-breadth curve (AUC-MB) to a panel of isolates will be computed for each participant with evaluable neutralization data at 2 weeks post boost.

*Secondary Analyses:* The analyses of magnitude-breadth described above are based on the endpoint area-under-the-curve, which is interpreted as the average  $\log_{10}$  IC50 to the set of isolates in the test panel. Use of this endpoint is maximally statistically powerful if one vaccine group has greater magnitude and breadth than the comparator vaccine group, but may miss an effect wherein one vaccine group has greater magnitude and the comparator vaccine group has greater breadth. Therefore, a secondary analysis may compare the distribution of magnitude-breadth curves among vaccine groups using the test statistic  $\max|B_d^G|$  from Huang, et al [35], which is designed to detect general differences in magnitude-breadth curve distributions.

#### 6.4.4.3 Analysis of binding Ab data

When a small panel of antigens (eg,  $\leq 5$ ) is being assessed in a multiplexed immunoassay, the response magnitudes and rates at 2 weeks post boost will be evaluated and compared for each antigen. When a larger panel is being assessed, in addition to assess each antigen separately, a summary measure across a group of similar antigens will be calculated, for example, a weighted-average may be constructed to account for the correlations between antigens as an integrate magnitude of responses to multiple antigens. Then this summary measure will be used in the multivariate linear model as the outcome variable to assess if this overall response measures differ by boost groups.

### 6.4.5 Analyses prior to end of scheduled follow-up visits

Any analyses conducted prior to the end of the scheduled follow-up visits should not compromise the integrity of the trial in terms of participant retention or safety or immunogenicity endpoint assessments. In particular, early unblinded analyses by treatment assignment require careful consideration and should be made available on a need to know basis only.

#### 6.4.5.1 Safety

During the course of the trial, unblinded analyses of safety data will be prepared approximately every 4 months during the main study, as defined in Section 3, for review by the SMB. Ad hoc safety reports may also be prepared for SMB review at the request of the HVTN 114 PSRT. The HVTN leadership must approve any other requests for unblinded safety data prior to the end of the scheduled follow-up visits.

#### 6.4.5.2 Immunogenicity

An unblinded statistical analysis by treatment assignment of a primary immunogenicity endpoint may be performed when all participants have completed the corresponding primary immunogenicity visit and data are available for analysis from at least 80% of these participants. Similarly, an unblinded statistical analysis by treatment assignment of a secondary or exploratory immunogenicity endpoint may be performed when all participants have completed the corresponding immunogenicity visit and data are available for analysis from at least 80% of these participants. However, such analyses for a secondary or exploratory immunogenicity endpoint will only take place after at least one of the primary immunogenicity endpoints of the same class (humoral, cell-mediated, innate or mucosal) or, if no primary endpoint of the same class, at least one of the primary immunogenicity endpoints reaches the aforementioned threshold. The Laboratory Program will review the analysis report prior to distribution to the protocol chairs, DAIDS, vaccine developer, and other key HVTN members and investigators. Distribution of reports will be limited to those with a need to know for the purpose of informing future trial-related decisions. The HVTN leadership must approve any other requests for HVTN immunogenicity analyses prior to the end of the scheduled follow-up visits.

## 7 Selection and withdrawal of participants

Participants will be healthy, HIV uninfected (seronegative) adults who comprehend the purpose of the study and have provided written informed consent. Volunteers will be recruited and screened; those determined to be eligible, based on the inclusion and exclusion criteria, will be enrolled in the study. Final eligibility determination will depend on results of laboratory tests, medical history, physical examinations, and answers to self-administered and/or interview questions.

Investigators should always use good clinical judgment in considering a volunteer's overall fitness for trial participation. Some volunteers may not be appropriate for enrollment even if they meet all inclusion/exclusion criteria. Medical, psychiatric, occupational, or other conditions may make evaluation of safety and/or immunogenicity difficult, and some volunteers may be poor candidates for retention.

Although myo/pericarditis has not been documented to occur with MVA, it has been an adverse effect associated with other vaccinia vaccines. This protocol includes cardiac surveillance measures to ascertain any association of myo/pericarditis with MVA vaccination. The eligibility criteria exclude potential participants with preexisting cardiac conditions, an accumulation of cardiac risk factors, baseline elevations in troponin, or clinically significant ECG findings that could complicate the conduct of the trial or compromise the detection of myo/pericarditis. Study clinicians are asked to carefully screen participants for signs and symptoms such as palpitations or poor exercise tolerance that might indicate preexisting cardiac conditions that could become symptomatic during the trial and be misattributed as effects of the study vaccines.

Determination of eligibility, taking into account all inclusion and exclusion criteria, must be made within 56 days prior to enrollment unless otherwise noted in Sections 7.1 and 7.2.

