## 5 Objectives and endpoints

### 5.1 Primary objectives and endpoints

*Primary objective 1:*

To evaluate the safety and tolerability of MVA/HIV62B and AIDSVAX B/E given separately or together as boost injections after prolonged immunologic rest, to participants who received MVA/HIV62B vaccinations in DDMM and MMM regimens in HVTN 205

*Primary endpoint 1:*

Frequency and severity of local and systemic injection site reactogenicity signs and symptoms, for each boost regimen

Laboratory measures of safety: white blood cells (WBC), neutrophils, lymphocytes, hemoglobin, platelets, ALT, AST, alkaline phosphatase, and creatinine

Frequency of AEs categorized by MedDRA System Organ Class, and MedDRA Preferred Term, severity and assessed relationship to study products; detailed description of all AE meeting DAIDS criteria for expedited reporting

Number of participants with early discontinuation of vaccinations and reason for discontinuation

*Primary objective 2:*

To compare HIV-specific antibody responses elicited by MVA/HIV62B and AIDSVAX B/E given separately or together as boost injections after prolonged immunologic rest

*Primary endpoint 2:*

Frequency, magnitudes and isotypes of Env-specific Ab responses for gp120, gp41, V1/V2, and the IDR of gp41 at 2 weeks after each boost

Neutralizing Ab titers and breadth against the Env vaccine strain (ADA) and heterologous tier 1 and tier 2 strains at 2 weeks after each boost

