## 6 Statistical considerations

### 6.1 Accrual and sample size calculations

Recruitment will target enrolling 100 healthy, HIV-uninfected participants previously enrolled into HVTN 205. Eligible participants will be assigned into one of 5 study groups (20 in each group) depending on their previous vaccine regimen received in HVTN 205. Participants previously vaccinated with DDMM will be randomized to receive MVA/HIV62B alone, AIDSVAX B/E alone, or a combination of MVA/HIV62B and AIDSVAX B/E given concurrently. HVTN 205 participants initially vaccinated with MMM will be randomized to be boosted with MVA/HIV62B alone or a combination of MVA/HIV62B and AIDSVAX B/E given concurrently.

Since enrollment is concurrent with receiving the first study vaccination, all participants will provide some safety data. However, for immunogenicity analyses, it is possible that data may be missing for various reasons, such as participants terminating from the study early, problems in shipping specimens, low cell viability of processed peripheral blood mononuclear cells (PBMCs), or high background. Immunogenicity data from 17 phase 1 and 2 phase 2a HVTN vaccine trials, which began enrolling after June 2005 (data as of September 2014), indicate that 10% is a reasonable estimate for the rate of missing data. For this reason, the sample size calculations in Section 6.1.2 account for 10% enrolled participants having missing data for the primary immunogenicity endpoints. To maximize the power of evaluating boosting regimens, Groups 1 and 3 with MVA/HIV62B-only boost and Groups 2 and 4 with MVA/HIV62B + AIDSVAX B/E boost will be combined in the primary analyses accounting for the prior priming regimens, in addition to analyses by each individual group. Interaction tests will be used to evaluate whether the effect of boosting regimens differs by the prior prime regimens. However, the study has low power to detect the interaction; therefore we will treat these interaction analyses as exploratory.

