#### 6.1.1 Sample size calculations for safety

The goal of the safety evaluation for this study is to identify safety concerns associated with product administration. The ability of the study to detect SAEs (Section 9) can be expressed by the true event rate above which at least 1 SAE would likely be observed and the true event rate below which no events would likely be observed. Specifically, for each vaccine group of the study ( $n = 20$ ), there is a 90% chance of observing at least 1 event if the true rate of such an event is 10.9% or more; and there is a 90% chance of observing no events if the true rate is 0.5% or less. For vaccine groups 1 and 3 combined and groups 2 and 4 combined ( $n = 40$ ), there is a 90% chance of observing at least 1 event if the true rate of such an event is 5.6% or more; and there is a 90% chance of observing no events if the true rate is 0.2% or less. As a reference, in HVTN vaccine trials from December 2000 through April 2014, about 4% of participants who received placebos experienced an SAE.

Probabilities of observing 0, 1 or more, and 2 or more events among groups of size 20 and 40 are presented in Table 6-1 for a range of possible true AE rates. These calculations provide a more complete picture of the sensitivity of this study design to identify potential safety problems with the vaccine.

**Table 6-1 Probability of observing 0 events, 1 or more events, and 2 or more events, among groups of size 20 and 40, for different true event rates**

| True event rate (%) | Pr(0/20) | Pr(1+/20) | Pr(2+/20) | Pr(0/40) | Pr(1+/40) | Pr(2+/40) |
|---------------------|----------|-----------|-----------|----------|-----------|-----------|
| 1                   | 81.8     | 18.2      | 1.7       | 66.9     | 33.1      | 6.1       |
| 3                   | 54.4     | 45.6      | 12        | 29.6     | 70.4      | 33.8      |
| 5                   | 35.8     | 64.2      | 26.4      | 12.9     | 87.1      | 60.1      |
| 7                   | 23.4     | 76.6      | 41.3      | 5.5      | 94.5      | 78        |
| 9                   | 15.2     | 84.8      | 54.8      | 2.3      | 97.7      | 88.6      |
| 10                  | 12.2     | 87.8      | 60.8      | 1.5      | 98.5      | 92        |
| 20                  | 1.2      | 98.8      | 93.1      | < 0.1    | > 99.9    | 99.9      |
| 30                  | 0.1      | 99.9      | 99.2      | < 0.1    | > 99.9    | > 99.9    |

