##### **6.4.3.2 AEs and SAEs**

AEs will be summarized using MedDRA System Organ Class and preferred terms. Tables will show by treatment group the number and percentage of participants experiencing an AE within a System Organ Class or within preferred term category by severity or by relationship to study product. For the calculations in these tables, a participant with multiple AEs within a category will be counted once under the maximum severity or the strongest recorded causal relationship to study product. Formal statistical testing comparing groups is not planned since interpretation of differences must rely heavily upon clinical judgment.

A listing of SAEs reported to the DAIDS Regulatory Support Center (RSC) Safety Office will provide details of the events including severity, relationship to study product, time between onset and last vaccination, and number of vaccinations received.

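### The cardiac surveillance is aimed at MVA, but no safety summary is planned for all 80 MVA-boosted participants

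*Combined protocol and SAP*

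**What the plan says.** - **Purpose.** Section 7 states: "This protocol includes cardiac surveillance measures to ascertain any association of myo/pericarditis with MVA vaccination". Section 9.4.1 likewise explains that the added cardiac monitoring is there to pick up cardiac effects of MVA.
- **Exposure.** Table 3-1 gives MVA/HIV62B to Groups 1 to 4 and saline in its place to Group 5. AIDSVAX B/E goes to Groups 2, 4 and 5. Section 6.1: "Recruitment will target enrolling 100 healthy, HIV-uninfected participants previously enrolled into HVTN 205", in five groups of 20.
- **Precision.** Section 6.1.1: "Probabilities of observing 0, 1 or more, and 2 or more events among groups of size 20 and 40 are presented in Table 6-1". The only pooling it names is "For vaccine groups 1 and 3 combined and groups 2 and 4 combined". Table 6-2 uses the same two sizes.
- **Analysis.** Section 6.4 adds analyses that combine groups across prior priming regimens, which again means 1+3 and 2+4. Section 6.4.3.2: "Tables will show by treatment group the number and percentage of participants experiencing an AE within a System Organ Class". It plans no formal tests between groups.
- **Endpoints.** Section 5.1 lists: "Laboratory measures of safety: white blood cells (WBC), neutrophils, lymphocytes, hemoglobin, platelets, ALT, AST, alkaline phosphatase, and creatinine". Troponin and ECG are not in the list; after enrolment both are done only when clinically indicated (Sections 9.4.1.2 and 9.4.1.3).

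**The concern.** The surveillance question is about a product, and the reporting is by regimen. Nothing in Sections 6.1.1 or 6.4.3 gives an event count, denominator and interval for everyone who received the MVA boost, nor for everyone who received AIDSVAX B/E. The report would therefore quote bounds for 20 or 40 participants on a question that 80 can inform.

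A smaller gap goes with it. Section 6.4.3.2 counts a participant once within a MedDRA category, so someone with two cardiac symptoms coded to different categories appears in two rows. Some of the symptoms asked about in Section 9.4.1.1, such as fatigue, chills and myalgia, are also solicited reactogenicity items in the first days (Sections 9.10 and 9.10.1) and so go to another table. The number of participants who had any symptom-triggered cardiac evaluation cannot be read from the planned tables. If it is not defined beforehand, it would be defined after unblinding.

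**Working it through.** **Inputs.** Five groups of 20 (Table 3-1), hence any MVA = 4 × 20 = 80, any AIDSVAX = 3 × 20 = 60, no MVA boost = 20. The interval is the two-sided 95% score interval that Section 6.1.1 uses.

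**Formulas.** Upper score bound for 0/n = z²/(n + z²), with z² = 1.96² = 3.84. True rate giving a 90% chance of at least one event = 1 − 0.1^(1/n). Chance of at least one event at true rate p = 1 − (1 − p)^n.

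**The plan's figures reproduce.** 3.84/23.84 = 16.1% for n = 20 and 3.84/43.84 = 8.8% for n = 40, as in Table 6-2. The 90% rates are 10.9% and 5.6%, matching "at least 1 event if the true rate of such an event is 10.9% or more" and "at least 1 event if the true rate of such an event is 5.6% or more". Every row of Table 6-1 also reproduces.

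**The same formulas for the product pools:**

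| n | who | upper bound, 0 events | 90% chance of ≥1 event |
|---|---|---|---|
| 20 | one group | 16.1% | 10.9% |
| 40 | pair 1+3 or 2+4 | 8.8% | 5.6% |
| 60 | any AIDSVAX | 6.0% | 3.8% |
| 80 | any MVA | 4.6% | 2.8% |

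Against the planned pairs, the bound is 8.76/4.58 = 1.9 times wider than it need be for MVA and 8.76/6.02 = 1.5 times for AIDSVAX. At a true rate of 1%, the chance of seeing at least one event is 33% in 40 and 55% in 80; at 2% it is 55% and 80%.

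**Short enrolment.** Section 6.1.2 considers 12 per group. The bounds are then 3.84/15.84 = 24.2% per group (as stated there), 3.84/27.84 = 13.8% for a pair of 24, and 3.84/51.84 = 7.4% for 48 MVA recipients.

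**What a comparison with Group 5 could show.** Two-sided Fisher exact test, with 0/20 in Group 5:

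- Groups 1 to 4: 14/80 gives p = 0.066 and 15/80 gives p = 0.037, so 15 events (19%) are needed.
- Groups 3+4: 7/40 gives p = 0.084 and 8/40 gives p = 0.043, so 8 events (20%) are needed.
- Power for 80 against 20, with a true rate of zero in Group 5: about 0% at an MVA rate of 5%, 1% at 10%, 65% at 20%.
- With no events anywhere, the 95% interval for the difference (Newcombe) is −16.1 to +4.6 points for 80 against 20, and −16.1 to +8.8 for 40 against 20.

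The gain in precision thus comes from the pool of 80, not from the contrast with 20.

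**The case against.** The strongest reply is that detection does not depend on these tables. Appendix I treats myocarditis and pericarditis as one reportable entity. Any episode at any grade is reported at once and as an SAE (Section 9.4.1.4), all are expedited (Section 11.2.3), and SAEs are listed individually with relationship and timing (Section 6.4.3.2). The SMB sees unblinded data about every 4 months and pools across protocols with similar vaccines (Section 11.1.2). Reporting by regimen is also reasonable, because MVA/HIV62B with AIDSVAX B/E had not been given together to humans (Section 4.8). And a bound of 4.6% adds little beside no MVA-associated cases in approximately 400 earlier recipients (Section 9.4.1), which by the same formula gives 3.84/403.84 = 0.95%, taking the number as exactly 400.

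Most of this stands. It shows that case-level detection is covered. It does not supply a denominator or interval for MVA in this trial's final analysis, and SMB review is monitoring, not that analysis.

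A reader might infer more than the documents support:

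- *That precision is thrown away, or that the trial could not state a bound for MVA.* By-group counts with denominators can be added to x/80. The summary is unspecified; the data are intact.
- *That myo/pericarditis cases would be scattered over the tables.* The reporting rules above prevent this. Only the triggering symptoms can be spread.
- *That troponin is left out.* Appendix F lists it among the safety labs done locally, so Section 6.4.3.3 arguably covers it. Because post-enrolment troponin and ECG are not scheduled, their absence from the Section 5.1 list is not in itself an error.

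**Conclusion.** The point holds as a gap in the descriptive safety summary. For the product at which the surveillance is aimed, the widest planned pool is 40 where 80 are available. The zero-event bound is 8.8% instead of 4.6%, and the rate with a 90% chance of at least one event is 5.6% instead of 2.8%. This assumes full enrolment and that an average rate over MVA alone and MVA with AIDSVAX is of interest.

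A reader might take the missing analysis to be a test of 80 exposed against 20 unexposed. The documents do not support that, for three reasons. Group 5 is drawn only from DDMM recipients, and MMM recipients have no arm without MVA, so only Groups 3+4 against Group 5 is a randomised comparison. Group 5 is not MVA-naive: every participant had 2 or 3 MVA injections in HVTN 205 (Section 4.8.1.1), so it lacks only the new boost. And neither comparison can confirm or exclude a rare association, since 15/80 or 8/40 events would be needed for p ≤ 0.05.

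**What to change.** In Section 6.4.3.2, beside the by-group tables:

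1. Add a descriptive any-MVA summary (Groups 1 to 4, n = 80) and an any-AIDSVAX summary (Groups 2, 4 and 5, n = 60), with score 95% intervals.
2. In the MVA summary, count each participant once for any cardiac evaluation triggered by symptoms, and once for a suspected, probable or confirmed case by Appendix I. Section 9.4.1.4 points to Appendix G for that case definition; correct the reference.
3. Show Groups 3+4 beside Group 5 as the randomised, DDMM-only comparison, with intervals and no formal test, in line with the existing decision not to test AEs.
4. State that Group 5 lacks only the new MVA boost, and that neither the pool nor the comparison can confirm or exclude a rare association.

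Add n = 60 and n = 80 to Tables 6-1 and 6-2.

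The cost is a few tables from data already collected, with no new visits, tests or clinical rules. The downside is that pooling averages over MVA alone and MVA with AIDSVAX and could mask a risk confined to the combination, which is why the by-group tables stay.

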### 7.1 Inclusion criteria

#### General and Demographic Criteria

1. **Age** of 18 to 55 years
2. **Prior participation in HVTN 205** with assignment to treatment (not placebo) arm:
  - a. Assigned to HVTN 205 Group 1 or Group 3, and received all 4 scheduled vaccinations (2 injections of pGA2/JS7 DNA (months 0, 2) and 2 injections of MVA/HIV62 (months 4, 6)); OR
  - b. Assigned to HVTN 205 Group 4, and received at least vaccinations 1, 2 and 4 (3 injections of MVA/HIV62 at months 0, 2 and 6).
3. **Access to a participating HVTN CRS** and willingness to be followed for the planned duration of the study
4. Ability and willingness to provide **informed consent**

5. **Assessment of understanding:** volunteer demonstrates understanding of this study; completes a questionnaire prior to first vaccination with verbal demonstration of understanding of all questionnaire items answered incorrectly
6. **Willing to be contacted** 2 years following initial study injection.
7. **Agrees not to enroll in another study** of an investigational research agent
8. **Good general health** as shown by medical history, physical exam, and screening laboratory tests

**HIV-Related Criteria:**

9. Willingness to receive **HIV test results**
10. Willingness to discuss HIV infection risks and amenable to HIV risk reduction counseling.
11. Assessed by the clinic staff as being at **“low risk” for HIV infection** and committed to maintaining behavior consistent with low risk of HIV exposure through the last required protocol clinic visit.

**Laboratory Inclusion Values**

**Hemogram/CBC**

12. **Hemoglobin**  $\geq 11.0$  g/dL for volunteers who were born female,  $\geq 13.0$  g/dL for volunteers who were born male
13. **White blood cell count** = 3,300 to 12,000 cells/mm^3
14. **Total lymphocyte count**  $\geq 800$  cells/mm^3
15. **Remaining differential** either within institutional normal range or with site physician approval
16. **Platelets** = 125,000 to 550,000/mm^3

**Chemistry**

17. **Chemistry panel:** ALT, AST, and alkaline phosphatase  $< 1.25$  times the institutional upper limit of normal; creatinine  $\leq$  institutional upper limit of normal.
18. **Cardiac Troponin T or I (cTnT or cTnI)** does not exceed the institutional upper limit of normal

**Virology**

19. **Negative HIV-1 and -2 blood test:** Participants must have a negative test result for HIV infection following the HVTN Lab Program’s in-study HIV testing algorithm, prior to initial enrollment.

20. **Negative Hepatitis B surface antigen (HBsAg)**

21. **Negative anti-Hepatitis C virus Ab (anti-HCV)**, or negative HCV polymerase chain reaction (PCR) if the anti-HCV is positive

